7.1 Objectives

7.1.1 Primary objectives

Part A: To assess the safety and tolerability of single ascending oral doses of BEN8744 in healthy subjects

Part B: To characterise the effect of food on the pharmacokinetic (PK) profile of at least 1 dose of BEN8744

Part C: To assess the safety and tolerability of multiple ascending oral doses of BEN8744 in healthy subjects

7.1.2 Secondary objectives

Part A: To assess the PK profile of BEN8744 after single oral doses in healthy subjects

Part B: To assess the safety and tolerability of a single dose of BEN8744 following high-fat food intake relative to fasting conditions in healthy subjects

Part C: To assess the PK profile of BEN8744 after repeated oral doses in healthy subjects

7.1.3 Exploratory objective

Part B (and optional in Part C):

To measure BEN8744 in urine and determine renal clearance in healthy subjects*

Exploratory characterisation of BEN8744 and its metabolites in plasma, urine, and faeces[†]

*If significant amounts of the parent compound are detected in Part B, the parent compound may be measured in Part C (in urine at 2 dose levels [low and high]).

[†]Faeces will be analysed in Part B only. If significant amounts of metabolites are detected in Part B, exploratory metabolite analyses may be conducted in Part C (in plasma and urine at 2 dose levels [low and high] on Day 1 and Day 14).

7.2 Endpoints

7.2.1 Primary endpoints

Safety and tolerability (Parts A and C): vital signs (blood pressure, pulse rate, tympanic temperature, and respiratory rate), 12-lead electrocardiogram (ECG), cardiac telemetry (Part A only), physical examination, laboratory safety tests (haematology, clinical chemistry, and urinalysis), adverse events (AEs), and Observer's Assessment of Alertness/Sedation scale (OAAS/S), visual analogue scale (VAS) to monitor sedation, and C-SSRS (Part C only).

PK (Part B): C_{max} , t_{max} , AUC_{24} , AUC_{72} , AUC_{last} , AUC_{inf} , % AUC_{extrap} , $t_{1/2}$, λ_Z , CL/F , V_Z/F

7.2.2 Secondary endpoints

PK (Part A): C_{max} , t_{max} , AUC_{24} , AUC_{72} , AUC_{last} , AUC_{inf} , $\%AUC_{extrap}$, $t_{1/2}$, λ_Z , CL/F , V_z/F

Safety and tolerability (Part B): vital signs (blood pressure, pulse rate, tympanic temperature, and respiratory rate), 12-lead ECG, physical examination, laboratory safety tests (haematology, clinical chemistry, and urinalysis), AEs, and OAAS/S and VAS to monitor sedation.

PK (Part C): C_{max} , t_{max} , C_{trough} , AUC_{tau} , AUC_{last} , AUC_{72} , AUC_{inf} , $\%AUC_{extrap}$, $t_{1/2}$, λ_Z , CL_{ss}/F , V_z/F , $R_{ac(AUC)}$, $R_{ac(Cmax)}$, $SR_{(AUC)}$

7.2.3 Exploratory endpoints

PK (Part B and optional in Part C): Ae_{72} , $f_e \cdot F$, CL_R

8 Overall trial design

8.1 Trial design

This is a Phase 1, FTIH, single-centre, randomised, double-blind, placebo-controlled, dose escalation trial to assess the safety and tolerability, PK, and food effect of BEN8744 in healthy subjects.

The trial will be in 3 parts: Part A will investigate single ascending oral doses of BEN8744; Part B is a 2-way crossover assessment of the effect of food on the PK of BEN8744; and Part C will investigate multiple ascending oral doses of BEN8744.

A schematic diagram of the study design is in section 8.2.

8.1.1 Part A

Enrolment of up to 64 healthy subjects is planned, in up to 5 groups (Groups A1–A5) and 3 optional groups (Groups A6–A8). Each group will consist of 8 subjects.

Subjects will receive a single dose of BEN8744 or placebo, as capsules, after an overnight fast of at least 10 h. At each dose level, 6 subjects will receive BEN8744 and 2 will receive matching placebo in an overall ratio of 3:1.

The starting dose for Group 1 is 2 mg BEN8744 or placebo. It is intended that subsequent cohorts will receive higher doses. The planned doses are in Table 6.

Table 6: Planned doses in Part A

Group	Dose of BEN8744
A1	2 mg
A2	6 mg
A3	20 mg
A4	60 mg
A5	100 mg
A6 (optional)	TBC
A7 (optional)	TBC
A8 (optional)	TBC

Additional intermediate or higher dose levels may be explored in 3 optional groups (Groups A6–A8). The dose levels will be selected by the safety review group (SRG) as described in section 8.5.

The dose will not be escalated unless the safety and tolerability of the previous dose are acceptable, and the conditions in section 8.5 are met. There will be an appropriate interval between sequential groups, to allow for review of those data.

Because BEN8744 has never been given to humans before, each new ascending dose will be staggered: 2 sentinel subjects will be dosed first, and the remaining subjects will be dosed at least 23 h later. To maintain the blind nature of the study, the 2 sentinel subjects will be randomised to ensure that 1 subject receives active treatment and the other receives placebo. Since one subject will receive placebo treatment, the sentinel subjects may be dosed at least 5 min apart. Provided the investigator considers the safety and tolerability in the sentinel subjects to have been acceptable, the remaining subjects will be dosed, at intervals of at least 10 min.

If the dose level selected is no higher than one that has already been shown to cause no safety concerns, sentinel subjects will not be required, and subjects will be dosed at intervals of at least 10 min.

Subjects will be screened within 28 days before their (first) dose of trial medication. Subjects will be resident on the ward from 1 day before their dose (Day –1) until up to 72 h after dosing (Day 4). They will return for a follow-up visit 7 (± 2) days after their inpatient stay (Day 11 ± 2 days).

8.1.2 Part B

Enrolment of up to 12 healthy subjects is planned, in up to 2 groups (Groups B1 and B2).

Each subject in Part B will have 2 study sessions (Sessions 1 and 2), in which they will receive a single dose of BEN8744, by mouth. Each subject will receive BEN8744 after an overnight fast of at least 10 h in one session, and after an FDA high-fat breakfast (1,013 kcal, 59.2 g fat [of which 28.1 g saturated fat]) in the other session; the order will be randomised 1:1, as shown in Table 7. A subject's doses

will be separated by a washout of at least 7 days (or 5 half-lives as determined in Part A, whichever is longer). Subjects dosed on the same day may be dosed at intervals of at least 10 min.

Table 7 Treatment sequence for each group (n=6 each) in Part B

	Session 1	Session 2
n=3 subjects	Fed	Fasted
n=3 subjects	Fasted	Fed

The dose to be tested in Group B1 will be decided following review of the interim safety, tolerability, and PK data from at least 3 dose levels in Part A, as described in section 8.5.3.

To reduce the risk of unexpectedly high plasma concentrations, the dose selected for Group B1 will be no higher than 50% of the highest dose tested in Part A that caused no safety concerns.

Group B2 is optional and may be required if the Sponsor decides to test the effect of food at an additional dose level (for example, if absorption and hence exposure is not proportional to dose in Part A) or under different conditions (eg with different fasting requirements or after a different meal such as a standard breakfast). The dose and food requirements for Group B2 will be decided following review of the interim safety, tolerability, and PK data from Group B1 and all available data from Part A.

Subjects will be screened within 28 days before their first dose of trial medication. Subjects will be resident on ward from 1 day before their dose (Day -1) until up to 72 h after dosing (Day 4). They will return for a follow-up visit 7 (± 2) days after their inpatient stay in Session 2 (Day 11 ± 2 days).

8.1.3 Part C

Enrolment of up to 32 healthy subjects is planned, in up to 3 groups (Groups C1–C3) and 1 optional group (Group C4). Each group will consist of 8 subjects.

Each subject will receive daily doses of BEN8744 or placebo, by mouth, for 14 days. At each dose level, 6 subjects will receive BEN8744 and 2 will receive matching placebo. Doses will be taken once or twice daily in the fasted state, unless emerging data indicate they should be taken in the fed state.

[figure not shown]
Part C will not start until at least 3 dose levels have been completed in Part A, as described in section 8.5.4. Part C may also be conducted in parallel with Part B. The dose, dosing regimen (once or twice daily), and whether the dose is taken fed or fasted, will be determined based on review of the available safety, tolerability and PK results from Parts A and B, and previous groups in Part C, as described in section 8.5.

The first total daily dose (ie, morning plus evening dose, if a twice-daily dosing regimen is chosen) tested in Part C (Group C1) will be the same as, or lower than, a single dose that has been given in Part A without any safety concerns. See also section 8.5.

[figure not shown]
[figure not shown]
[figure not shown]
Subjects will be screened within 28 days before their first dose of trial medication. Subjects will be resident on ward from the day before their dose (Day -1) until up to 72 h after their final dose (Day 17). They will return for a follow-up visit 7 (± 2) days after their inpatient stay (Day 24 ± 2 days).

8.2 Study flow chart

Figure 4: Schematic of the overall study design

Note: Dose 1 in Part A will be 2 mg. Subsequent doses will be decided by the safety review group. Doses in Parts B and C will be decided by the safety review group after at least 3 dose levels have been investigated in Part A.

Figure 5: Schematic of the study design of Parts A, B, and C**Part A****Part B****Part C**

8.3 Definition of the end of the trial

The end of the trial is defined as the final follow-up visit by the last subject. If the trial is terminated prematurely, the trial ends when the sponsor notifies the investigator in writing that the trial has finished, or when the last subject attends the final follow-up visit, whichever is later.

8.4 Stopping criteria

8.4.1 *Trial stopping criteria*

The trial will be stopped if either of the following occurs:

- 1 or more SAEs considered to be at least possibly related to study treatment; or
- 2 or more severe or clinically significant adverse events (AEs) that are considered to be at least possibly related to study treatment at any dose level.

In Parts A and C, treatment allocations may be unblinded to aid safety review, provided that the unblinding is appropriately documented. In Part B, all subjects will receive BEN8744.

If, after an internal safety review, it is appropriate to restart the trial, a substantial amendment will be submitted to the MHRA and research ethics committee (REC). The trial will not restart until the amendment has been approved by the MHRA and REC.

8.4.2 *Dose escalation stopping criteria*

A dose level will not be repeated, or exceeded, if:

- the results of safety tests for that dose level give the sponsor or investigator cause for concern,
- the investigator or sponsor considers that dose level to be poorly tolerated.

In addition, a dose level will not be exceeded if:

- plasma concentrations at higher doses in any individual subject are predicted to exceed the exposure threshold (see section 8.5).
- 1 or more Hy's Law cases; Hy's Law is defined as alanine aminotransferase (ALT) and/or aspartate aminotransferase (AST) elevations $\geq 3 \times$ upper limit of normal (ULN) in the presence of a total bilirubin increase $\geq 2 \times$ ULN in the absence of other findings of cholestasis such as a significant increase in alkaline phosphatase (ALP) and without an alternative diagnosis that could explain the increase in ALT/AST and bilirubin.

- 2 or more subjects have a mean QTcF of > 500 msec or increase from baseline of > 60 msec

The trial will be stopped if any criterion in section 8.4.1 is met.

Dosing will be discontinued in an individual subject if any criterion in section 9.4.2 is met.

8.5 Criteria for dose selection

8.5.1 **Review of data by the Safety Review Group**

During the study, the dose will be increased only if the safety, tolerability, and PK of the previous dose are acceptable.

All doses will be selected by the Safety Review Group (SRG), which will include (as a minimum) the principal investigator (or delegate) and the sponsor's medically qualified representative (or delegate). Each dose decision will be made and documented in line with HMR standard operating procedures (SOPs).

Before selecting a new dose level (for any group), the SRG will review, as a minimum, the safety, tolerability, and PK data from the previous dose level and (if different) the highest dose level tested to date, as described below. Safety, tolerability, and PK data obtained from the previous group(s) will also be reviewed, if applicable. All data used to support dose selection will be quality checked.

Review of safety and tolerability data

The SRG will review (as a minimum) safety and tolerability data, up to 48 h after final dosing, from at least 4 evaluable subjects who have received active treatment at the highest dose level tested to date. An evaluable subject is one who completes dosing and has undergone procedures until 24 h after final dosing, and had no major protocol deviations. To maintain blinding, data from at least 6 of the 8 subjects in each group must be reviewed to ensure that the dataset includes at least 4 evaluable subjects on active treatment. If fewer subjects than planned are dosed, any subjects required to complete the group may be dosed in parallel with subsequent groups.

The safety data reviewed will include, as a minimum:

- AEs and SAEs, including description, frequency, intensity, onset, duration, and relationship to treatment
- physical examinations
- vital signs
- 12-lead safety ECG
- telemetry (Part A)
- laboratory safety tests

- C-SSRS (Part C)

Review of pharmacokinetic data

The SRG will review (as a minimum) PK data up to at least 24 h after final dosing from at least 4 evaluable subjects on active treatment at the highest dose level tested to date before the dose is escalated.

When PK data are reviewed, dummy-subject identifiers will be applied to the data by the bioanalytical laboratory, or an unblinded programmer at HMR, so that individual data may be reviewed without unblinding the sponsor and investigator. If fewer subjects are dosed than planned, to avoid potential unblinding, individual data will not be reviewed – mean, minimum and maximum data will be reviewed, and number of subjects will not be presented. If there are missing PK data at a particular timepoint, the missing data may be replaced by an interpolated value to maintain blinding.

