Subjects who meet the above criteria will be considered discontinued from dosing. However, the investigator may ask the subject to continue their participation in the study, so they can be monitored for safety and PK, or the investigator may withdraw the subject from the trial.

9.4.3 *Replacement of withdrawn subjects*

Withdrawn subjects will be replaced at the discretion of the sponsor and investigator. Subjects withdrawn because of AEs considered possibly related to study treatment (see section 14.2) will not be replaced. Replacements for other withdrawn subjects will receive the treatments intended for the withdrawn subject, from the start of the trial. For subjects in Part B, the sponsor and investigator will decide which sessions the replacement subject will complete.

10 *Treatments*

10.1 *Treatments administered*

In Part A, subjects will receive a single oral dose of BEN8744 or placebo.

In Part B, subjects will receive a single oral dose of BEN8744 on 2 different occasions, separated by a washout of at least 7 days.

In Part C, subjects will receive once or twice-daily oral doses of BEN8744 or placebo for 14 days.

Fasting requirements are described in section 11.

All treatments will be administered orally with approximately 240 mL of water. All treatments will be given in the fasted state in Parts A, and in the fasted or fed state in Part C.

10.2 *Overdose*

Symptoms of overdose of BEN8744 are not yet known. In the case of accidental overdose, subjects should be treated symptomatically as no specific antidote is available.

10.3 *Blinding (Parts A and C only)*

The trial medication will be repackaged and relabelled by the HMR Pharmacy, according to the randomisation schedule. Active and placebo treatments will be labelled such that it is not possible to distinguish between them. If the expiry dates of placebo and active treatment differ, both treatments will be labelled with an expiry

date no later than the earlier of the 2 expiry dates. Each subject's treatment will be given a unique code number, traceable to the batch number of the medication.

The placebo and active treatments for each group will be identical in appearance, and similar in taste and smell. To maintain the blind nature of the trial, the same number of capsules will be given to each subject in a group.

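### In Part C, the minimum dataset for raising the dose need not include a subject stopped early for toxicity, and reviewing 6 of 8 subjects secures 4 evaluable active subjects only if all six are evaluable

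*Combined protocol and SAP*

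**What the plan says.** Section 8.5.1 of the protocol requires the SRG to review safety data "from at least 4 evaluable subjects who have received active treatment at the highest dose level tested to date". It defines the term: "An evaluable subject is one who completes dosing", who also has procedures done to 24 h after the last dose and no major deviation. No exception is made for a subject who stops because of toxicity.

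Because the SRG is blinded, the section turns this into a count that can be checked without the code: "data from at least 6 of the 8 subjects in each group must be reviewed", with the stated purpose "to ensure that the dataset includes at least 4 evaluable subjects on active treatment".

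Part C (section 8.1.3) gives 14 days of dosing to groups of 8: "At each dose level, 6 subjects will receive BEN8744 and 2 will receive matching placebo". Section 9.4.2 lists individual stopping criteria (related SAE, QTcF, and several liver criteria) and then says: "Subjects who meet the above criteria will be considered discontinued from dosing". Section 9.4.1 also lets the investigator withdraw a subject for intolerance. Section 9.4.3 rules out replacing a subject withdrawn for a possibly related AE.

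**The concern.** A Part C subject stopped before the last dose has not completed dosing and so is not evaluable. Two things follow from the wording.

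First, the subject who showed the toxicity does not count towards the minimum and may be one of the two left unreviewed. Second, if that subject is one of the six, the count of six no longer delivers what section 8.5.1 says it delivers.

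Safety and tolerability are the primary objective of Part C, and the SRG's review decides whether the next group gets a higher dose. A minimum built from completers leans towards subjects who tolerated the dose under review.

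**Working it through.** **Inputs.** 8 per group, 6 active and 2 placebo (section 8.1.3); minimum of 4 evaluable active subjects; at least 6 of 8 reviewed; evaluable means dosing completed, procedures done to 24 h after the final dose, and no major deviation (all section 8.5.1).

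**The plan's own figure.** If all 8 subjects are evaluable, the worst set of six contains both placebo subjects: 6 − 2 = 4 active. The figure of 4 is reproduced. Five reviewed would give only 5 − 2 = 3, so six is the smallest number that works and there is no slack.

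**One active subject stopped early.** There are C(8,2) = 28 ways to choose the two subjects left out. The group is now 5 completing active, 1 stopped active and 2 placebo.

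| Two left out | Sets | Stopped subject reviewed? | Evaluable active among the six |
|---|---|---|---|
| Two completing active | C(5,2) = 10 | yes | 3 |
| One completing active, one placebo | 5 × 2 = 10 | yes | 4 |
| Both placebo | 1 | yes | 5 |
| Stopped subject, one completing active | 5 | no | 4 |
| Stopped subject, one placebo | 2 | no | 5 |
| Total | 28 | | |

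- *Stopped subject included:* 10 + 10 + 1 = 21 sets, of which 10 hold only 3 evaluable active subjects. Over all sets this is 10/28 = 36%.
- *Stopped subject left out:* 5 + 2 = 7 sets, all with at least 4. Each contains at least one placebo subject, because the five completing active subjects alone make only 5 of 8. The written minimum is met without the toxicity data.

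If the stopped subject is on placebo, the worst case is still 4, but a blinded SRG would not know that.

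**Larger review sets.** With one active subject stopped, reviewing 7 gives a worst case of 7 − 2 − 1 = 4, and reviewing all 8 gives 5.

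**Do other rules close the one-stop case?** Compare the individual criteria with the rules on the trial and on escalation:

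- Related SAE: section 8.4.1 stops the trial after one, so this case is closed.
- QTcF: section 9.4.2 stops one subject at the threshold; section 8.4.2 needs two or more subjects at the same threshold.
- Liver: section 8.4.2 bars escalation after one Hy's Law case; section 9.4.2 also stops a subject for ALT ≥ 5 × ULN alone, or ALT ≥ 3 × ULN with rash or hepatitis symptoms.
- Intolerance (section 9.4.1): one non-serious case meets no numeric rule in 8.4.1 or 8.4.2.

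So a single stop that is neither a related SAE nor a Hy's Law case triggers no numeric rule. What remains is judgement.

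**The case against.** The strongest reply is that section 8.5.1 sets floors. The SRG may review all 8 subjects, and nothing tells it to leave a stopped subject out. It includes the principal investigator or a delegate, who would very probably know of the stop. Section 8.4.2 bars repeating or exceeding a dose if safety results cause concern or the dose is judged poorly tolerated, and neither clause is limited to evaluable subjects. All of this stands, and it limits the consequence. It does not make the written minimum sound, because the judgement may rest on a minimum dataset that omits the relevant subject. The section's opening does refer to data from the previous dose level in general, but it points to the minimum set out below it.

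It can also be said that the requirement for 4 evaluable active subjects stands by itself, so a set yielding 3 still fails it. That is right. But the count of six is the means section 8.5.1 gives a blinded SRG for knowing that the safety requirement is met, and here it gives the wrong assurance. The PK review has the same minimum and passes through staff who hold the code, so a shortfall might surface there; the text does not say that this is checked.

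A reader might go further and infer that toxicity would be concealed, or that the trial's safety results are biased by survivor selection. The documents do not support either. The safeguards above exist, and sections 16.2.3 and 16.2.6 summarise safety in everyone who received at least one dose. Nor is 36% a probability of failure, since nobody draws six of eight at random.

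With two active subjects stopped, 28 − C(4,2) = 22 of 28 sets fall short, but that figure should carry little weight. Section 14.1 normally treats an AE leading to withdrawal of drug as significant. If section 8.4.1 is read in that sense (its term is not identical), two related AE stops would already have stopped the trial.

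**Conclusion.** The point holds as a defect in the required minimum dataset for escalation in Part C. The claim that six of eight secures 4 evaluable active subjects fails once one active subject among the six is not evaluable: the guaranteed number drops from 4 to 3. If that subject is left out, the minimum is met without the data that matter most.

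This rests on reading *completes dosing* literally, and on a single stop that is neither a related SAE nor a Hy's Law case. In Part A the single dose is complete once taken, so selection by early stopping of dosing is a Part C matter. How often such a stop would occur cannot be derived from the documents, and the conclusion does not need it. The change should be made: it concerns a stated safeguard on raising the dose, and it is cheap.

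**What to change.** Change two sentences in section 8.5.1:

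1. Require the SRG to review all available safety data from every subject dosed at that level, including any who stopped dosing early. Completing dosing then sets only the count for adequate exposure, and no longer limits the safety data reviewed.
2. Replace "data from at least 6 of the 8 subjects in each group must be reviewed" with a requirement for data from at least 6 evaluable subjects. Any six evaluable subjects include at most 2 on placebo, so at least 6 − 2 = 4 are on active treatment, and the blind is kept.

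No new data collection is needed, and no dose or stopping rule changes. A group of 8 can absorb two non-evaluable subjects (8 − 2 = 6). With three or more, at most 5 evaluable subjects remain, and the blinded count cannot be met without replacement, which section 9.4.3 does not allow after withdrawal for a possibly related AE. The text should therefore say how the 4 evaluable active subjects are then confirmed, for example by the unblinded programmer already provided for in the PK review.

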A sealed copy of the randomisation code will be kept in a locked file in the HMR Pharmacy. A copy will also be kept by the bioanalytical laboratory. The investigator will be supplied with sealed envelopes, each one containing the treatment allocation for the subject whose number appears on the outside of the envelope. Those envelopes will be kept in the trial master file, readily accessible to clinical staff. Emergency procedures for revealing medication codes are specified in section 10.4.

The investigators, medical monitor and clinical monitor will remain blinded throughout the trial, unless safety concerns necessitate unblinding (see section 10.4 below).

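### Section 8.5.1 hides individual PK data only when fewer subjects are dosed than planned, so a fully dosed group with one missing profile reveals that subject's allocation

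*Combined protocol and SAP*

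**What the plan says.** The allocation within a group is fixed and stated openly. Section 8.1.1 (Part A) says "At each dose level, 6 subjects will receive BEN8744 and 2 will receive matching placebo in an overall ratio of 3:1", and section 8.1.3 (Part C) says "At each dose level, 6 subjects will receive BEN8744 and 2 will receive matching placebo". In Part A, section 10.5 adds that the sentinel pair is one active and one placebo.

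Section 8.5.1 has dummy identifiers put on the PK data "so that individual data may be reviewed without unblinding the sponsor and investigator". Individual profiles are therefore the default display. The exception is: "If fewer subjects are dosed than planned, to avoid potential unblinding, individual data will not be reviewed". In that case the SRG sees only the mean, minimum and maximum, and the number of subjects is withheld. A further provision allows an interpolated value where a single timepoint is missing.

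The SRG includes at least the principal investigator and the sponsor's medically qualified representative (section 8.5.1). Section 10.3 says: "The investigators, medical monitor and clinical monitor will remain blinded throughout the trial, unless safety concerns necessitate unblinding".

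**The concern.** The plan recognises that a short count of profiles can unblind, and it has a display that prevents this. The display is tied to the number of subjects dosed, whereas the information leaks through the number of profiles shown. The two can differ:

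- Under section 8.5.1 an evaluable subject must complete dosing and have procedures to 24 h after the final dose, so a dosed subject can fail to be evaluable.
- Part C doses for 14 days. A subject who meets a criterion in section 9.4.2 gets no further doses, and so has no full-course Day 14 profile.
- Under section 9.4.1, data collection stops when a subject withdraws, and the subject may ask for identifiable samples to be destroyed.

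In each case all 8 subjects were dosed, so the masking does not apply. Interpolating a timepoint cannot supply a whole profile. The ward knows who stopped.

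Replacement would restore the count, but it is discretionary, and section 9.4.3 excludes one class: "Subjects withdrawn because of AEs considered possibly related to study treatment (see section 14.2) will not be replaced". The subject exposed may therefore be one who stopped for an adverse event. Later causality judgements made with that knowledge feed the drug-related TEAE summary (section 16.2.6.1) and the stopping criteria in section 8.4.1, such as "1 or more SAEs considered to be at least possibly related to study treatment".

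**Working it through.** **Inputs.** 8 subjects per group, 6 active and 2 placebo (sections 8.1.1 and 8.1.3). One active and one placebo in the Part A sentinel pair (section 10.5). Individual display unless fewer are dosed than planned (section 8.5.1). No dropout rate is stated anywhere.

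**The plan's own figure.** Section 8.5.1 says that reviewing 6 of the 8 subjects secures at least 4 on active. At most 2 of any 6 can be placebo, so the minimum is 6 − 2 = 4. The figure is right.

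**One known subject missing, Part C, all 8 dosed.**
- Missing subject on active: probability 6/8 = 0.75, and 5 active profiles are shown.
- Missing subject on placebo: probability 2/8 = 0.25, and 6 active profiles are shown.

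Each count fits only one allocation, so the subject's probability of being on active moves from 75% to 100% or 0%. The documents do not say whether placebo profiles are displayed. If they are, the contrast is 5 quantifiable plus 2 blank against 6 plus 1, and the conclusion is the same.

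**Two known subjects missing, Part C.** There are C(8,2) = 28 equally likely placements.
- 4 active profiles: C(6,2)/28 = 15/28 = 0.536; both were on active.
- 5 active profiles: 6 × 2/28 = 12/28 = 0.429; one of each, so each subject is at 50%.
- 6 active profiles: C(2,2)/28 = 1/28 = 0.036; both were on placebo.

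Both allocations are certain in (15 + 1)/28 = 57% of cases.

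**One known subject missing, Part A.**
- Sentinel: 5 or 6 profiles, each with probability 1/2. The sentinel is revealed, and the other sentinel with them.
- Non-sentinel: 5 profiles with probability 5/6 (on active), 6 with probability 1/6 (on placebo). In the second case the other five non-sentinels are all revealed as active.

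**How often a profile could be missing.** Let q be the proportion of Part C subjects without a Day 14 profile, assumed to be 2–5% and independent between subjects. P(at least one missing among n) = 1 − (1 − q)^n.

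| | q = 0.02 | q = 0.05 |
|---|---|---|
| One group, n = 8 | 1 − 0.98^8 = 0.149 | 1 − 0.95^8 = 0.337 |
| C1 and C2, n = 16 | 1 − 0.98^16 = 0.276 | 1 − 0.95^16 = 0.560 |

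C1 and C2 are used because, with groups C1–C3 run, these two are certain to be followed by an escalation review. The figures bound the leak from above: a replacement dosed before the review restores the count, and some two-missing cases do not reveal the allocations.

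**With the masking applied.** If the count is withheld, it carries no information. The missing subject stays at the prior: 6/8 in Part C, and in Part A 1/2 for a sentinel and 5/6 for a non-sentinel.

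**The case against.** The strongest objection is about timing. A withdrawal is barred from replacement because its event has been judged possibly related, so that judgement already exists. Section 8.5.1 also lists relationship to treatment among the data the SRG receives. The Day 14 PK review comes after a mid-course withdrawal, and section 8.4.1 does not wait for it. A reader might infer that the leak biases the original causality call and the stopping rule it feeds. The documents do not support that. What stands is an effect on later or revised calls and on the assessment of ongoing or subsequent events.

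Second, blinding is not absolute. Sections 8.4.1 and 10.4 allow codes to be broken to help safety decisions. Under section 8.4.1, however, that unblinding must be documented. This leak is neither decided on nor recorded.

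Third, the case is narrow. In Part A subjects take one supervised dose and stay on the ward for up to 72 h, so a dosed subject without a profile would be exceptional. In Part C a subject taken off dosing may stay on for PK monitoring, and some withdrawals can be replaced on the same treatment. The leak also needs the SRG to know whose profile is missing, which may not hold for a sample lost at the laboratory. All of this stands and limits frequency, but it does not close the gap.

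Fourth, dosed might be meant as completed dosing. Section 8.5.1 uses completing dosing as a separate notion when it defines an evaluable subject. If that was the intent, the same one-sentence edit settles it.

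A reader might also infer that, with the count withheld, the SRG cannot tell whether it has PK data "from at least 4 evaluable subjects on active treatment at the highest dose level tested to date before the dose is escalated". That does not follow. The 6-of-8 rule gives at least 4 active subjects without unblinding. It is stated for safety data, but the arithmetic serves PK equally.

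**Conclusion.** The concern holds as a gap in the wording of section 8.5.1. When all 8 subjects are dosed and one known subject has no profile, the display reveals that subject's allocation with certainty. With two missing in Part C, both are revealed in 57% of cases. This rests only on the fixed 6:2 split and on the SRG knowing who is missing. Part B is open-label and unaffected.

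The realistic setting is an unreplaced mid-course stop or withdrawal in Part C. There the chance of at least one missing profile is about 15–34% per group and 28–56% over C1 and C2. These are upper bounds on the leak, and they rest on the assumed 2–5%. A reader might extend the sum to all three planned Part C groups, but C3 leads to an escalation review only if the optional C4 is run.

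The change is worth making because the rule as written fails its own stated purpose. It does not call the primary safety results or causality calls already made into question.

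**What to change.** In section 8.5.1, replace the condition on subjects dosed with: *If PK profiles from fewer subjects than planned are available for the review, for any reason*. Leave the rest of that sentence as it is, with summary values only and the number of subjects withheld.

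Judge the condition on all 8 subjects of the group, active and placebo alike. If it were judged on active profiles only, the masking would come on only when the missing subject was on active, and the switch itself would give away the allocation.

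The cost is one sentence and no extra subjects, samples or staff. The downside is that the SRG sees summaries instead of individual profiles in a few more reviews. The maximum is still shown, so the exposure-limit checks in sections 8.5.2 and 8.5.4 remain possible, as they do under the summary display that the plan already accepts.
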